**Registration number: NCT04302350**

**October 25, 2020**

## Study Protocol

This study was registered at [www.ClinicalTrials.gov](http://www.ClinicalTrials.gov) (registration number: NCT04302350). The study protocol was approved by the Ethics Committee of The First Affiliated Hospital of Nanjing Medical University (Nanjing, Jiangsu province, China) and written consent was obtained from all participants. The study was conducted at The First Affiliated Hospital of Nanjing Medical University, Nanjing, China between January 15, 2020 and May 15, 2020.

We contacted patients aged 20-70 y, with an American Society of Anesthesiologists (ASA) physical grade I or II, a body mass index (BMI) between 18 and 30 kg/m^2, with early stage lung cancer (diameter of tumor consolidation  $\leq$  2cm, none evidence of lymph node or distant metastasis, c-stage IA1 or IA2)

[figure not shown]
(active limited resection) and patients at high risk due to poor general condition who cannot undergo lobectomy (c-stage IA1 to IA3) (passive limited resection). Exclusion criteria included a history of severe asthma or pneumothorax, pulmonary bullae on chest CT and patient refusal. High-resolution lung nodule CTA (Iopromide) and three-dimensional computed tomography bronchography and angiography (3D-CTBA) were applied to confirm nodules location and associated vessels and bronchi, and the simulated surgical path and resection range were confirmed before surgery.

Eligible subjects were randomly assigned to Group75, Group50 or Group0 at a 1:1:1 ratio. The order of allocation was generated by computer personnel that were not involved in trial through a computer program. Concealment was carried out using opaque envelopes, which were opened after the patients' arrival in operating room. Patients, surgeons, anesthesiologists, assessors, and statisticians were blinded to treatment allocation.

After admission, patients were routinely monitored for electrocardiogram, pulse oximetry, and invasive arterial blood pressure. When anesthesia induction was completed, intubation was carried out using an appropriate-size double-lumen endobronchial tube (DLT) under visual laryngoscope and the position of

the DLT was confirmed with fiberoptic bronchoscopy and adjusted as needed. OLV of the dependent lung with  $\text{FiO}_2=1.0$  was begun in the lateral position, by inflation of the bronchial cuff of the DLT, clamping the DLT to the nonventilated lung proximally and opening the distal port of the DLT lumen to the atmosphere. Tidal volumes were 5 mL/kg ideal bodyweight (male: height -100, and female: height - 105) without positive end expiratory pressure (PEEP). In order to avoid possible confounding effects of inhalation of volatile anesthetics on oxygenation, all subjects received total intravenous anesthesia.

According to preoperative 3D-CTBA evaluation of bronchial and vascular structure of pulmonary nodules and pulmonary segments, the target segmental bronchus, arteries and intra-segment veins were accurately identified and dissected by ligation or stapler cutting. After that, the anesthesiologist began to make preparations for the lung inflation. The portable nitrous oxide concentration detector (TD600-SH-B- $\text{N}_2\text{O}$ , tiandi shouhe, Beijing, China) was installed to detect  $\text{N}_2\text{O}$  concentration (vol%), and then adjusted the anesthesia machine to the manual control mode. The flow of the selected gas mixture was set to 8L/min (Group75 set to  $\text{N}_2\text{O}:\text{O}_2=6:2$ , Group50 set to  $\text{N}_2\text{O}:\text{O}_2=4:4$ , Group0 set to  $\text{O}_2=8$ ), avoiding the interference of the total gas flow. When the  $\text{N}_2\text{O}$  concentration detector reached the predetermined gas concentration, and then the collapsed lung was re-expanded completely with controlled airway pressure under 20 cmH2O (1cm H2O=0.098 kPa) by the anesthesiologist. This procedure took approximately 1 min, and then  $\text{FiO}_2=1.0$  was performed after the initiation of the OLV.

**Fig. 1** Consort flow diagram

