## Statistical Analysis Plan

A power analysis indicated a sample size of 48 patients were needed based on the following assumptions: (i)  $\alpha = 0.05$  (two-sided significance level); (ii)  $1-\beta = 0.9$ ; (iii) the appearance time of visible ISP is 5-12 min in view of previous study . Taking into consideration loss to follow-up and possible dropouts, 81 patients were ultimately enrolled.

The data collected were entered into a Microsoft Access database and then analyzed with SPSS software (version 24; IBM SPSS, Chicago, IL, USA). Primary outcome analysis was performed by one-way analysis of variance, and LSD-t test for pairwise comparison. Secondary outcome analyses included one-way analysis of variance for parametric variables (SPO2, PaO2 value, duration of surgery, total thoracic drainage, duration of drainage, postoperative hospital stay, lung function) and  $\chi$ -square tests for nonparametric variables (incidence of postoperative complications, ASA grades). P value <0.05 (both sides) was considered statistically significant. Univariate and multivariate linear regression analysis were used to determine the predictors for the intersegmental plane. The  $\beta$  value and 95% confidence interval (95% CI) of each of the significant variables were calculated.

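### The primary gas comparison leaves out entry route and ASA grade, both known before allocation, which may cost a little precision; ASA grade is also tested as if it were an outcome

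*Combined protocol and SAP*

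**What the plan says.** The eligibility paragraph of the Study Protocol opens with limits on age, ASA grade ("with an American Society of Anesthesiologists (ASA) physical grade I or II") and BMI, then describes two ways in. The first is active limited resection, for consolidation up to 2 cm with "none evidence of lymph node or distant metastasis, c-stage IA1 or IA2". The second is for "patients at high risk due to poor general condition who cannot undergo lobectomy (c-stage IA1 to IA3) (passive limited resection").

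On allocation, the Study Protocol states "Eligible subjects were randomly assigned to Group75, Group50 or Group0 at a 1:1:1 ratio" and "The order of allocation was generated by computer personnel that were not involved in trial through a computer program". It mentions no strata, blocks or minimisation.

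In the Statistical Analysis Plan, "Primary outcome analysis was performed by one-way analysis of variance, and LSD-t test for pairwise comparison". No covariate is named. A regression is also planned: "Univariate and multivariate linear regression analysis were used to determine the predictors for the intersegmental plane". Its candidate variables are not listed, and it is not tied to the comparison between gas groups. The secondary outcome analyses include chi-square tests for "nonparametric variables (incidence of postoperative complications, ASA grades").

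**The concern.** The protocol separates patients who could have had a lobectomy from patients who could not, and gives the two routes different stage limits. If route or general condition affects how quickly the intersegmental plane appears, that variation sits in the error term of the primary ANOVA. A chance imbalance between arms then moves the estimated gas contrasts. Both variables are fixed before allocation, so the analysis could use them at almost no cost.

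The handling of ASA grade is a separate matter and needs no assumption. Patients have their ASA grade before they are randomised. A chi-square test across arms can therefore pick up only chance, and a significant result would stand in the report as a secondary finding with no meaning.

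**Working it through.** **Inputs from the documents.** Three arms at 1:1:1 and 81 enrolled, so 27 per arm and 81 − 3 = 78 residual degrees of freedom. The appearance time of the plane, taken here as the primary outcome because the sample-size statement rests on it, is given as 5–12 min. No SD, passive-route share or route effect is given.

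**Assumed inputs.** Within-route SD s = (12 − 5)/4 = 1.75 min; passive share p from 10% to 30%; difference in mean appearance time between routes D from 1 to 3 min.

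**Variance removed by adjusting for route.** Variance inflation is V = 1 + p(1 − p)D²/s², with s² = 3.0625. The share removed by adjustment is 1 − 1/V.

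| p | D (min) | V | Variance removed |
|---|---|---|---|
| 10% | 1 | 1 + 0.09/3.0625 = 1.029 | 3% |
| 20% | 1 | 1 + 0.16/3.0625 = 1.052 | 5% |
| 20% | 2 | 1 + 0.64/3.0625 = 1.209 | 17% |
| 30% | 3 | 1 + 1.89/3.0625 = 1.617 | 38% |

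A 2 min effect is 2/1.75 = 1.14 within-route SDs, which is already large. The last row (3/1.75 = 1.71 SDs) is an outer bound. With no passive patients V = 1 and nothing is removed for route.

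**What this does to a confidence interval.** The half-width of a 95% interval for a pairwise contrast is about 1.99 × SD × √(2/27).
- Adjusted: 1.99 × 1.75 × 0.272 = 0.95 min.
- Unadjusted, p = 20% and D = 2: SD = 1.75 × √1.209 = 1.92, half-width 1.04 min. The difference is about 6 seconds.
- Unadjusted, p = 20% and D = 1: SD = 1.75 × √1.052 = 1.80, half-width 0.97 min. The difference is about 1.5 seconds.

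**Chance imbalance.** Suppose 16 of 81 patients (20%) are passive-route and are allocated at random to three arms of 27. A named pair of arms differs by 4 or more such patients in about 24% of allocations (exact enumeration: 23.5%). With 8 passive patients it is 11%, with 24 it is 30%. The chance that the largest and smallest of the three arms differ by 4 or more is 26%, 47% and 54% for 8, 16 and 24 patients, but that is a statement about any pair. At D = 2 a 4-patient difference shifts the contrast by 2 × 4/27 = 0.30 min. The SD of the chance shift is 2 × √(0.2 × 0.8 × 2/27) = 0.22 min.

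**Validity of the unadjusted test.** In 10,000 simulated trials per setting, with p = 30% and 27 per arm, the unadjusted ANOVA rejected a true null 4.9% of the time for route effects of both 0.5 and 1.0 SD.

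**Power.** Take an effect that gives 90% power at 16 per arm (48 in total). For p of 10–50% and route effects of 0.25–1.0 SD, power at 27 per arm is 99.2% unadjusted and 99.2–99.8% adjusted.

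**The case against.** The strongest reply is that nothing is wrong with the test. Randomisation makes the unadjusted contrast unbiased, and the ANOVA error term already carries the between-route variance. This stands in full. A reader might infer that pooling the two routes biases the gas comparison or inflates false positives; neither the documents nor the simulation supports that.

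The size also rests on inputs that the documents do not supply. Nothing in them links stage, ASA grade or route to appearance time. Planning a search for predictors is not the same as expecting these variables to be predictors. At moderate route effects (0.5 SD) the standard error grows by only 1–3%. This stands too, and it is why the point is minor. It would likewise be wrong to quote 47% as the risk to a particular contrast, since for a named pair the figure is about half that.

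Three further limits hold. That allocation is unstratified is inferred from silence. The ASA I–II limit opens the eligibility text and may bind both routes, so different fitness limits cannot be asserted firmly; the difference in stage limits and in fitness for lobectomy remains. And although no numerical lung-function limit is stated, severe asthma, pneumothorax and bullae are excluded.

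One part of the reply does not hold: that the planned multivariate regression already covers this. It could include group and patient factors, but its covariates are unlisted, it reports estimates for the significant variables only, and it is not the source of the primary contrast.

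**Conclusion.** The point holds as a cheap improvement in precision. The primary analysis as written is valid, and no conclusion of the trial is shown to depend on the change. With a within-route SD of 1.75 min, adjusting for route removes about 3–5% of variance for a 1 min route effect and 17% for 2 min at 20% passive, and nothing for route if that group is empty. Any gain from ASA grade cannot be sized from the documents.

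The ASA labelling error holds without assumptions, but it does not touch the primary contrast. Priority: minor.

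**What to change.** In the Statistical Analysis Plan, take the primary pairwise group contrasts from a linear model of appearance time on group plus two prespecified covariates, entry route (active or passive) and ASA grade. Drop a covariate that shows no variation. Keep the unadjusted one-way ANOVA as a supporting analysis. Remove ASA grade from the secondary outcome tests and report it descriptively by arm as a baseline characteristic.

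The cost is a change of wording, one extra model and up to two of 78 residual degrees of freedom. Both variables should be known from eligibility assessment, so enrolment and conduct do not change. One condition applies. The document is dated October 2020, after the stated study period ended in May 2020. The covariates count as prespecified only if they are fixed without sight of outcomes by group; otherwise the adjusted model should be labelled as added later.

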## Statistical Analysis Plan

A power analysis indicated a sample size of 48 patients were needed based on the following assumptions: (i)  $\alpha = 0.05$  (two-sided significance level); (ii)  $1-\beta = 0.9$ ; (iii) the appearance time of visible ISP is 5-12 min in view of previous study . Taking into consideration loss to follow-up and possible dropouts, 81 patients were ultimately enrolled.

The data collected were entered into a Microsoft Access database and then analyzed with SPSS software (version 24; IBM SPSS, Chicago, IL, USA). Primary outcome analysis was performed by one-way analysis of variance, and LSD-t test for pairwise comparison. Secondary outcome analyses included one-way analysis of variance for parametric variables (SPO2, PaO2 value, duration of surgery, total thoracic drainage, duration of drainage, postoperative hospital stay, lung function) and  $\chi$ -square tests for nonparametric variables (incidence of postoperative complications, ASA grades). P value <0.05 (both sides) was considered statistically significant. Univariate and multivariate linear regression analysis were used to determine the predictors for the intersegmental plane. The  $\beta$  value and 95% confidence interval (95% CI) of each of the significant variables were calculated.

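### SpO2, PaO2 and postoperative complications are judged by an omnibus P value alone, with no planned difference or interval for either N2O arm against Group0

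*Combined protocol and SAP*

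**What the plan says.** In the Statistical Analysis Plan, the secondary analyses put SpO2 and PaO2 under one-way ANOVA, in the same list as duration of surgery, drainage, hospital stay and lung function. Complications fall under chi-square "tests for nonparametric variables (incidence of postoperative complications, ASA grades"). One threshold serves every outcome: "P value <0.05 (both sides) was considered statistically significant".

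LSD-t pairwise comparison is attached to the primary outcome only. The one place where an interval is planned is the regression for predictors of the intersegmental plane, where the "95% confidence interval (95% CI) of each of the significant variables were calculated".

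The power statement (two-sided alpha 0.05, power 0.9) rests on a single clinical input: "the appearance time of visible ISP is 5-12 min in view of previous study". It gives 48 patients, and "81 patients were ultimately enrolled".

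In the Study Protocol, the inflation gas is delivered at 8 L/min in all arms, with N2O:O2 at 6:2 in Group75, 4:4 in Group50, and oxygen only in Group0. Inflation takes about 1 minute, after which one-lung ventilation resumes at FiO2 1.0.

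**The concern.** The arms differ in inspired oxygen by design. If N2O has a cost, SpO2, PaO2 and complications are where one would look for it, and the case for a faster-appearing plane depends partly on that cost being small. An omnibus P value returns only significant or not significant. It does not say which arm differs from Group0, by how much, or what size of disadvantage the data leave open.

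No power was assigned to these outcomes, so a non-significant result could arise with no harm or with a harm of some size, and the specified outputs would not separate the two. What is at stake is the statement the trial can make about oxygenation and complications. The primary analysis is not affected.

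**Working it through.** **Inputs from the documents.** Three arms at 1:1:1; 81 enrolled, so 81/3 = 27 per arm if all are analysed; 48 in the power statement, so 48/3 = 16 per arm; two-sided alpha 0.05. Oxygen fraction during inflation: 2/8 = 25%, 4/8 = 50%, 8/8 = 100%.

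**Inputs assumed.** The documents give no SD for SpO2 or PaO2, no complication rate and no harm margin. Shifts are therefore expressed in SD units, and complication rates are illustrative.

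**The plan's own figure.** The 48 cannot be reproduced from what is stated, because 5-12 min is neither a difference nor an SD. One assumed pair does give 16 per arm: SD 1.75 min (7/4, a quarter of the range) with one arm differing by 2 min. The 2 min is not in the documents. In any case the 48 concerns appearance time and carries no information on power for the other outcomes.

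**SpO2 and PaO2, one-way ANOVA.** Power comes from the noncentral F with 2 and 3(n-1) df and noncentrality λ = n Σ(μᵢ - μ̄)²/σ².
- One arm shifted by d SD (or both N2O arms shifted equally from Group0): λ = n·d²·2/3. For d = 0.5, n = 27: 27 × 0.25 × 2/3 = 4.5.
- Evenly graded arms with extreme difference d: λ = n·d²/2. For d = 0.5, n = 27: 27 × 0.25/2 = 3.375.

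| Shift (SD), n = 27 per arm | Power, evenly graded | Power, one or both arms shifted |
|---|---|---|
| 0.3 | 15% | 18% |
| 0.5 | 35% | 45% |
| 0.8 | 74% | 86% |
| 1.0 | 91% | 97% |

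Power reaches 50% at 0.53 SD (one or both arms shifted) to 0.62 SD (graded). At 16 per arm, power for 0.5 SD is 21-27%.

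**Complications, three-arm chi-square, n = 27 per arm.** Simulated power with one arm raised and the other two at the lower rate:
- 10% to 20%: about 16%
- 10% to 30%: about 49%
- 5% to 15%: about 21%

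If both N2O arms are raised instead, exact enumeration gives 14%, 43% and 16%. If the rise is graded across arms, it gives 12%, 35% and 14%.

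**What an interval would show.**
- Mean difference, pooled error: half-width = t(0.975, 78) × √(2/27) = 0.54 SD. At 16 per arm it is 0.71 SD.
- Risk difference with 3/27 in each arm (P = 1.0): each Wilson interval is about 3.9% to 28.1% around 11.1%. The Newcombe half-width is √[(0.111 - 0.039)² + (0.281 - 0.111)²] ≈ 0.184, so the 95% CI runs from -18 to +18 percentage points.
- With 0/27 events in an arm, the exact two-sided 95% upper limit is 1 - 0.025^(1/27) = 12.8%.

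**The case against.** A reader might infer that this plan will declare N2O harmless whenever P exceeds 0.05, and that a real harm would usually be missed. The documents do not support either step as a general statement. The plan defines what counts as significant; it does not say that a non-significant result will be called no difference or safe. It declares no safety, equivalence or non-inferiority objective, and it does not label these outcomes as harms. That reading of them rests on the oxygen fractions in the protocol.

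Nor is a miss the usual result for every harm. An SpO2 or PaO2 shift of 0.8 SD would be detected in roughly three-quarters or more of trials, and one of 1.0 SD in more than nine out of ten. Nothing in the documents shows which shift matters clinically. Inflation lasts about a minute, FiO2 1.0 follows, and no sampling time for SpO2 or PaO2 is stated, so the expected shift could be large or negligible. The complication rates used here are also assumptions.

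Secondary outcomes are often unpowered, and that alone is not a fault. The text is also brief: its silence on descriptive reporting does not rule out arm means, SDs and counts from which a reader could derive intervals.

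All of this stands, and it limits the claim. It does not supply what is missing: no difference or interval against Group0 is specified for these outcomes, and pairwise testing is written for the primary outcome only.

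**Conclusion.** The point holds in limited form. For SpO2, PaO2 and complications, the specified outputs are omnibus P values, and these cannot show how much harm remains compatible with the data.

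At 27 per arm, a miss is more likely than not for oxygenation shifts below about 0.53-0.62 SD. It is also more likely than not for each complication increase examined, although 10% to 30% in one arm, at 49% power, is close to even. These figures assume that all 81 are analysed in equal arms, and they rest on assumed shifts and event rates. If only 48 were evaluable, power would be lower.

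This is a gap in what the analysis will report. It is not evidence of harm, and it is not a finding that the plan draws a false conclusion. The change is worth making because it is cheap and alters what the trial can say about oxygenation and complications.

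**What to change.** In the secondary analyses of the Statistical Analysis Plan, specify two comparisons, Group75 v Group0 and Group50 v Group0:
- SpO2 and PaO2: the mean difference with its 95% CI.
- Postoperative complications: the risk difference with a 95% CI by the Newcombe or an exact method.

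Add a sentence to this effect: *P>0.05 on these outcomes will not be interpreted as absence of harm; any statement on oxygenation or complications will give the largest harm that the 95% CI does not exclude.*

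The document is dated October 2020 and the study ran from January to May 2020. If the intervals are added after the data were seen, label them as such.

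The cost is SAP wording and two interval estimates per outcome from data already collected. No margin and no further patients are needed. The downside is that the intervals will be wide (about ±0.54 SD for the continuous outcomes, about ±18 points at 3/27 v 3/27), so any safety statement becomes less favourable than a bare non-significant P value would suggest.

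### Giving coefficients and confidence intervals only for significant predictors is expected to overstate weak predictors and to hide null results

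*Combined protocol and SAP*

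**What the plan says.** The closing sentences of the Statistical Analysis Plan introduce the regression: "Univariate and multivariate linear regression analysis were used to determine the predictors for the intersegmental plane". They then state what is produced from it, namely that the beta "value and 95% confidence interval (95% CI) of each of the significant variables were calculated". The only threshold in the section is a general one: "P value <0.05 (both sides) was considered statistically significant".

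The available sample is given in the same section: "81 patients were ultimately enrolled". The Study Protocol adds that there are three arms: "Eligible subjects were randomly assigned to Group75, Group50 or Group0 at a 1:1:1 ratio".

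For the regression, the plan gives no list or number of candidate variables and no rule linking the univariate and multivariate steps. It does not say whether randomised group is in the model, and it mentions no multiplicity adjustment, shrinkage or validation. The response variable is not named either. I take it to be the time to appearance of the intersegmental plane, since that is the quantity behind the sample-size statement.

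**The concern.** Estimating and showing an effect only when it is significant is selection on the result. A weak predictor passes the threshold mainly in samples where chance has pushed its estimate away from zero, so the estimates that appear are too large on average. The usual 95% interval takes no account of that selection. A variable with no effect that passes by chance is presented with an interval excluding zero, which is its true value. Variables that do not pass get no estimate, so a reader cannot tell what was examined, or separate good evidence of little effect from an imprecise result.

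At stake is the credibility of whatever is named a predictor. With 81 patients, covariates of modest influence fall in the range where the filter does most damage.

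**Working it through.** **Inputs.** From the Statistical Analysis Plan: n = 81 enrolled (an upper limit on the number analysed) and a two-sided threshold of 0.05. Assumed, because the plan gives none: the strength of the true associations, the number of candidates and the correlations among them. The plan states no figure for the regression, so there is none to reproduce first.

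**1. Where the filter cuts.** In a simple linear regression with n = 81, a slope is significant when |t| exceeds 1.990 on 79 degrees of freedom. As a sample correlation this is

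r = t / √(t² + n − 2) = 1.990 / √(3.960 + 79) = 0.219.

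No smaller sample correlation is reported. If the true correlation is 0.10, even the smallest reportable one is 0.219 / 0.10 = 2.2 times the truth. At a true correlation of 0.30 the cut lies below the truth, so estimates on both sides of it can be reported.

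**2. Average effect of the filter alone.** Simulated simple regressions with n = 81, keeping only slopes with P < 0.05 and using no screening step:

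| True correlation | Chance of being reported | Mean reported slope ÷ truth | Coverage of reported 95% CI |
|---|---|---|---|
| 0.10 | 15% | 2.7 | 81% |
| 0.15 | 27% | 1.9 | 91% |
| 0.20 | 44% | 1.5 | 94% |
| 0.30 | – | 1.13 | 97% |
| 0.40 | – | 1.02 | 97% |
| 0.47 | – | 1.00 | 95% |

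For a true correlation of zero, coverage among reported results is 0% by construction: P < 0.05 and a 95% interval that excludes zero are the same event.

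**3. Adding a univariate screen (an assumed procedure).** Ten candidates, one of them a true predictor, pairwise correlation 0 or 0.3, a univariate P < 0.05 screen, then a multivariable model showing only P < 0.05 variables:

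- standardised beta 0.1: 2.6 to 2.7 times the truth, coverage 82% to 85%;
- beta 0.2: 1.5 times, coverage 94% to 95%;
- beta 0.3: 1.10 to 1.13 times, coverage 97% to 98%;
- beta 0.5: 0.91 to 0.99 times, coverage 95% to 97%.

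The pattern matches step 2, so the point does not depend on whether a screen is used.

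**4. False predictors.** For k independent null candidates, each tested at 0.05, the chance of at least one is 1 − 0.95^k: 23% for k = 5, 34% for 8, 40% for 10 and 54% for 15. In the two-step simulation with all candidates null, at least one of nine noise variables was reported in 25% (correlation 0.3) to 37% (correlation 0) of runs. The formula for nine independent tests gives 1 − 0.95^9 = 37%.

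**5. The alternative.** In the two-step data sets, fitting all ten candidates and reporting every coefficient gave mean estimates of 0.098 to 0.106 for a true beta of 0.1, 0.198 to 0.203 for 0.2 and 0.296 to 0.300 for 0.3. Coverage was 94.6% to 95.3% in all settings.

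**The case against.** The strongest reply is that the harm depends on assumptions the documents do not settle. If the candidates that matter are strong, the filter does almost nothing: from a correlation of about 0.3 the inflation is 13% or less and coverage is near or above nominal. At 0.20, coverage is still 94%. This stands. Inflation is an expected bias for weak effects and is not guaranteed for every reported coefficient; with correlated candidates and a screen, strong effects were even slightly attenuated.

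Two further inferences are tempting and unsupported. A reader might conclude that univariate P values decide entry to the multivariate model. The text names both kinds of regression but gives no linking rule, and a univariate table beside a full multivariable model would fit the sentence equally well. A reader might also conclude that randomised group is left out. The plan is silent on that, and silence is a gap in specification rather than evidence of omission.

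It can also be said that the regression is subsidiary. The primary comparison is a separate one-way analysis of variance with LSD-t pairwise tests, and the documents state no conclusions, so predictors cannot be called one of the trial's findings. That limits the importance of the point. It does not answer it, because the restriction to significant variables is written into the plan.

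**Conclusion.** The point holds in a limited form and should be corrected. The plan ties beta and its interval to significance. With 81 patients this is expected to overstate weak predictors about 2.7-, 1.9- and 1.5-fold at true correlations of 0.10, 0.15 and 0.20, to give false positives intervals that always miss the truth, and to leave null results unseen. Effects of about 0.3 or more are little affected, so a strong effect of the gas mixture would probably not be exaggerated.

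The 23% to 54% chance of at least one false predictor rests on an assumed 5 to 15 independent null candidates, each tested once at 0.05. The inflation figures assume a linear model with normal errors and all 81 patients analysed.

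A reader might infer that the trial's main result is compromised. It is not: the primary analysis of variance does not use this regression.

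**What to change.** Replace the rule about significant variables with one linear model of appearance time. Include randomised group as two indicators, plus a short list of baseline covariates chosen without reference to their P values. Age, BMI and ASA grade are available as eligibility variables. Lung function qualifies only if it was measured before surgery; the plan lists it among the secondary outcomes without giving its timing. With those four covariates, one term each, the model has 1 + 2 + 4 = 7 parameters and leaves 81 − 7 = 74 residual degrees of freedom.

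Report every coefficient with its 95% confidence interval, significant or not, and state how many candidates were considered. Give the covariate-adjusted group differences as a supplement to the analysis of variance.

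Label the covariate results exploratory and not prespecified. The Study Protocol says the trial ran from January 15 to May 15, 2020, and the document is dated October 25, 2020, so a list chosen now cannot be called fixed in advance.

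The cost is a change of wording and one more model run, with no new data. The downside is fewer highlighted predictors.
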